1. INR
2. Platelets

The physician investigator will review all laboratory results and those that are clinically significant.

Drug-drug Interaction Management Plan:

A letter will be sent to the subject's primary care physician to inform them of the subject's study participation and the possibility of concomitant medication restrictions.

Individual subjects on the active study drug who will have acute medical conditions that require the use of a new non-study drug will have to be assessed by a study provider to ensure that there is no drug interaction with ibutamoren. A study provider will contact the subject and investigate the non-study medication:

Subject discontinuation criteria:

Subjects will be discontinued from Aim 1 of the study if they develop

1. Glucose homeostasis criteria: Please refer to the "**Monitoring Glucose Homeostasis**" section on page 25. This protocol prevents unnecessary discontinuations for spuriously elevated single fasting glucose results.
2. Positive pregnancy test
3. Severe / intolerable side effects of ibutamoren
4. Development of malignancy
5. Initiation of the following medications: OCPs, pioglitazone, or strong CYP3A4 inhibitors
6. Liver-related discontinuation criteria as outlined per the section below titled *Liver-related Adverse Event Assessment and Drug Induced Liver Injury Monitoring*.

Liver-related Adverse Event Assessment and Drug Induced Liver Injury (DILI) Monitoring:

Liver-related adverse events (AEs) will be graded on the Common Terminology Criteria for Adverse Events (CTCAE), Version 5. Abbreviations that follow include alkaline phosphatase (ALP), alanine aminotransferase (ALT), aspartate aminotransferase (AST) and total bilirubin (TB).

Drug stop, drug induced liver injury (DILI) monitoring and subject discontinuation rules: For individual subjects, drug will be stopped if the subject develops any of the following:

(1) Study drug will be stopped with the potential for restart for the following criteria outlined below (CTCAE Grade 2 and additional DILI Monitoring Guideline Criteria) regardless of relationship to ibutamoren mesylate.

- Liver-related CTCAE Grade 2 AE based on ALP, ALT, AST or TB
 - Alkaline phosphatase: Between 2.5 and 5x ULN if normal baseline or between 2.5 and 5x baseline if baseline was abnormal.
 - ALT or AST: Between 3 and 5x ULN if normal baseline or between 3 and 5x baseline if baseline was abnormal.
 - TB: Between 1.5 and 3x ULN if normal baseline or between 1.5 and 3x baseline if baseline was abnormal (i.e. in Gilbert's).
- Additional DILI Monitoring Guideline Criteria[76]
 - ALT \geq 300 U/L, regardless of baseline
 - ALT \geq 2x baseline if abnormal with liver-related symptoms, including severe fatigue, nausea, vomiting and/or RUQ pain

Repeat liver function testing (including ALT, AST, ALP and TB) will be repeated in 2-5 days and subject will be referred to patient's clinician to evaluate for other etiologies of abnormal liver function tests per DILI Consensus Guideline recommendations. Study

drug can only be restarted if alternative etiology identified and liver enzymes return to baseline (e.g. after episode of viral illness). It is expected that resolution and drug restart will occur within 14 days of drug discontinuation.

(2) Study drug will be stopped without the potential for restart for any liver-related CTCAE AE grade 3 or higher based on ALP, ALT, AST, TB or clinical symptoms criteria, regardless of relation to ibutamoren mesylate. These include:

- Alkaline phosphatase, ALT or AST: Greater than 5x ULN if normal baseline or greater than 5x baseline if baseline was abnormal.
- TB: Between 3 x ULN if normal baseline or greater than 3x baseline if baseline was abnormal.
- Clinical evidence of hepatic failure, including asterixis, mild encephalopathy, drug-induced liver injury, limiting self-care ADL, evidence of portal vein flow abnormalities associated with varices and/or ascites.

Subjects will be discontinued from the study at this time without possibility of drug restart.

Study discontinuation rules: Study discontinuation will be considered if any of the following occur, including (1) three subjects develop the same Grade 3 CTCAE attributed to ibutamoren mesylate; (2) two subjects develop any Grade 4 CTCAE attributed to ibutamoren mesylate; or (3) any one patient develops a Grade 5 CTCAE.

If any of these patient or study discontinuation criteria are met, the clinical data will be reviewed by the data safety monitoring board (DSMB) for safety. An agreement will be reached regarding any additional safety monitoring or protocol changes. Minutes recorded during any such DSMB meeting will be recorded and sent to the FDA for review.

C. Adverse Events Reporting

All adverse events will be reported to the IRB in a timely manner according to the guidelines provided by Partner's Human Subjects Research Committee.

All treatment emergent serious adverse events will be documented and reported immediately to the IRB at General Brigham, as well as to the DSMB. An event that is serious must be recorded on the case record and requires expeditious handling to comply with regulatory requirements. In the event that a patient becomes ill or injured as a direct result of participation in the research study, necessary medical care will be made available. All adverse effects will be reported as per Mass General Brigham requirements. Potentially serious adverse events (SAEs) will be followed to resolution or stabilization and reported as SAEs if they become serious. Necessary dates related to the subject's SAE will be provided [REDACTED] ensure proper report, record, and documentation of the subject's SAE.

A serious adverse event is one that meets any one of the following criteria:

- Fatal or life-threatening
- Requires inpatient hospitalization
- Results in persistent or significant disability or incapacity
- Congenital anomaly
- Important medical event that may jeopardize the patient or require intervention to prevent serious outcome
- Cancer
- Overdose
- Results in development of drug dependency or drug use

12. References

1. Younossi, Z.M., et al., *Global epidemiology of nonalcoholic fatty liver disease-Meta-analytic assessment of prevalence, incidence, and outcomes*. Hepatology, 2016. **64**(1): p. 73-84.
2. Wong, R.J., et al., *Nonalcoholic steatohepatitis is the second leading etiology of liver disease among adults awaiting liver transplantation in the United States*. Gastroenterology, 2015. **148**(3): p. 547-55.
3. Charlton, M.R., et al., *Frequency and outcomes of liver transplantation for nonalcoholic steatohepatitis in the United States*. Gastroenterology, 2011. **141**(4): p. 1249-53.
4. Chaves, V.E., F.M. Junior, and G.L. Bertolini, *The metabolic effects of growth hormone in adipose tissue*. Endocrine, 2013. **44**(2): p. 293-302.
5. Sesmilo, G., et al., *Effects of growth hormone administration on inflammatory and other cardiovascular risk markers in men with growth hormone deficiency. A randomized, controlled clinical trial*. Ann Intern Med, 2000. **133**(2): p. 111-22.
6. Villares, R., et al., *Inhibitory Role of Growth Hormone in the Induction and Progression Phases of Collagen-Induced Arthritis*. Front Immunol, 2018. **9**: p. 1165.

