8. Significant alcohol use, defined as >2 drinks/day (14/week) in women or >3 drinks/day (or 21/week) in men
9. Aspartate or aminotransferase levels >300 U/L, suggesting liver disease other than NAFLD/NASH.
10. Other known liver disease, for example, autoimmune or viral hepatitis, hemochromatosis or alcoholic fatty liver disease.
11. Evidence of hepatobiliary and hepatic impairment such as:
 - a. INR >1.3
 - b. TB >1.5 mg/dL (with exception of Gilbert's with elevation of indirect bilirubin in the presence of direct bilirubin of < 0.4 mg/dL)
 - c. Albumin <3.5 g/dL
 - d. Platelet count $<150,000$ /uL
 - e. Historical or screening biopsy consistent with cirrhosis
 - f. Imaging suggestive of cirrhosis (e.g., splenomegaly, varices, nodular appearance of liver, radiographic evidence of ascites)
 - g. History of clinical events of liver decompensation such as variceal bleeding, presence of ascites, etc.
12. Pregnancy or breastfeeding.
13. Known pituitary or hypothalamic disease affecting the growth hormone axis
14. Regular use of drugs causing hepatic steatosis in the past 12 months (chronic oral steroids, methotrexate, tamoxifen)
15. Use of medications that may impact study endpoints, such as pioglitazone or Vitamin E.
16. Treatment with medications without acceptable alternative that may interact with ibutamoren, including:
 - a. Moderate or strong inhibitors of CYP3A4.

- b.** Moderate or strong inducers of CYP3A4.
- c.** Medications known to act as strong inhibitors of P-glycoprotein (P-gp).

17. Unsuitable for study per investigator discretion

18. Known HIV Diagnosis

B. Source of Subjects and Recruitment Methods

Recruitment will be performed by study personnel, including research coordinators, nurse practitioners and physician staff. To maximize enrollment of subjects, subjects will be recruited from a large population of patients with NAFLD through the following locations and the following resources:

- 1) Prior participants with overweight/obesity who have participated in Neuroendocrine Unit research studies
- 2) MGH Fatty Liver and GI Clinics
- 3) MGH NAFLD Cohort
- 4) [REDACTED] Research Patient Data Registry (RPDR) [REDACTED]

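### The liver stopping rules list the same high ALT values as both restartable and non-restartable, and no precedence is stated

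*Combined protocol and SAP*

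**What the plan says.** The rules are in Section 10.B, under Liver-related Adverse Event Assessment and Drug Induced Liver Injury (DILI) Monitoring.

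- **Rule (1), restart possible.** It opens: "Study drug will be stopped with the potential for restart for the following criteria outlined below". For ALT or AST its Grade 2 entry is "Between 3 and 5x ULN if normal baseline or between 3 and 5x baseline if baseline was abnormal". A further entry, taken from a DILI guideline, adds ALT at or above "300 U/L, regardless of baseline". The restart condition is that "drug can only be restarted if alternative etiology identified and liver enzymes return to baseline". Viral illness is the example given, and restart is expected within 14 days.
- **Rule (2), no restart.** It reads "Study drug will be stopped without the potential for restart for any liver-related CTCAE AE grade 3 or higher". The ALT threshold is "Greater than 5x ULN if normal baseline or greater than 5x baseline if baseline was abnormal". The participant is then discontinued from the study.

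The list of safety assessments and the subject discontinuation criteria, both also in Section 10.B, send the reader to this section for action on liver tests. Nothing visible in it says which rule applies when a value meets both. No ULN for ALT is given anywhere in the documents.

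**The concern.** The Grade 2 bands in rule (1) stop at five times the reference value, which is where rule (2) begins, so those two parts fit together. The 300 U/L entry has no upper limit and so runs on into rule (2)'s range. An ALT value in that range is listed once as a stop that may be reversed and once as a stop that may not.

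What is at stake is re-exposure after a marked ALT rise. Take a normal-baseline participant who reaches 320 U/L during a viral illness and then recovers. At an assumed ULN of 40, this is above 5 × 40 = 200. One clinician could cite rule (1) and its restart condition; another could cite rule (2) and discontinue. A safety rule of this kind should not depend on inference.

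**Working it through.** The plan states no figure to reproduce, so the check applies the two rules as written.

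**Inputs**
- Rule (1), absolute entry: ALT ≥ 300, any baseline, no upper limit.
- Rule (1), Grade 2 entry: 3R ≤ ALT ≤ 5R.
- Rule (2): ALT > 5R.
- R is the ULN if baseline was normal, and the participant's own baseline if it was abnormal.
- ULN is not in the documents. The values from 30 to 65 U/L used here are assumptions.

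**Where both rules apply.** Both hold when ALT ≥ 300 and ALT > 5R. The 300 entry has no cap, so any ALT of 300 or more that satisfies rule (2) also satisfies rule (1). A grid of ULN 30 to 65, baseline 10 to 300 and ALT from 300 to just under 2000 gave no exception.

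The overlap starts at exactly 300 when 5R < 300, that is when R < 300/5 = 60. For R ≥ 60 it starts just above 5R.

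| R (U/L) | 5R | ALT of exactly 300 falls under | Overlap starts |
|---|---|---|---|
| 30 | 150 | both rules | at 300 |
| 40 | 200 | both rules | at 300 |
| 55 | 275 | both rules | at 300 |
| 59 | 295 | both rules | at 300 |
| 60 | 300 | rule (1) only | just above 300 |
| 65 | 325 | rule (1) only | just above 325 |
| 80 | 400 | rule (1) only | just above 400 |
| 100 | 500 | rule (1) only | just above 500 |
| 200 | 1000 | rule (1) only | just above 1000 |
| 300 | 1500 | rule (1) only | just above 1500 |

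Rows up to 65 can be read as an assumed ULN with normal baseline. Any row above the ULN can be read as an abnormal baseline.

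**Ordering.** With normal baseline and an assumed ULN of 40, whole-number ALT values from 201 to 299 meet rule (2) only, so restart is barred. Values of 300 or more meet rule (2) and are also listed as restartable. The higher value thus carries the more permissive listing.

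**If rule (2) always prevails.** For R < 60, every ALT of 300 or more already exceeds 5R. The 300 entry then has no effect for a normal-baseline participant at any ULN below 60, although it is written to apply whatever the baseline. It adds a stop that the Grade 2 band does not already give only when 300 < 3R, that is when R > 100.

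**The case against.** The strongest reply is that the rules are tiered. Both require the drug to be stopped. Rule (1) only permits a restart, under conditions, while rule (2) covers any liver event of Grade 3 or higher and bars restart twice over. Not restarting complies with both lists; restarting after a Grade 3 value breaches rule (2). The 300 U/L entry also has a clear use of its own as an absolute limit where multiples of a high baseline run far up. At a baseline of 270, for instance, 3 × 270 = 810 and 5 × 270 = 1350, so ALT of 300 meets rule (1) only.

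Most of this stands. It makes rule (2) the likelier reading, and it shows that the 300 entry is not redundant for high abnormal baselines. It does not supply the missing statement of precedence. Review by the DSMB once a discontinuation criterion is met is provided for, but the text does not say that this settles which list applies. A redacted block under Monitoring Liver Function Testing might contain a clarification. However, the section to which the protocol sends the reader for action is legible and has none.

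A reader might infer three stronger points, which the documents do not support:

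- **The stop collides with eligibility.** Exclusion 9 in Section 4 removes "Aspartate or aminotransferase levels >300 U/L, suggesting liver disease other than NAFLD/NASH", while the stop begins at 300. The two coincide at exactly 300 and nowhere else, and the stop is worded for a value that a participant develops. A baseline of 270 does reach 300 with an 11% rise (300/270 = 1.11), but little room below a fixed limit is a design choice. Section 10 describes baseline elevations as mild and does not tie its remark on fluctuation to values near 300. It also provides two pre-treatment measurements.
- **The overlap costs completers.** No event rate is given. Enrolment is 12 or 15, depending on the section, for 10 completers, and Section 9 allows for 2 dropouts from 12 and specifies sensitivity analyses for missing data. Nothing shows that the overlap adds any loss.
- **A ULN of 60 or more removes the conflict.** That is true only of ALT at exactly 300, as the table shows.

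**Conclusion.** The contradiction is real and narrow. Any ALT of 300 U/L or more that exceeds five times the ULN (normal baseline) or five times an abnormal baseline is listed under both rules, with opposite restart status. At exactly 300 this requires a reference value below 60 U/L; at 60 or above the overlap moves up to just beyond five times that value. That some overlap exists does not depend on the ULN. Only its starting point does, and the ULN values used here are assumptions.

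Rule (2) is probably meant to prevail, but this is an inference from its wording. The point is a minor safety-wording correction. It does not affect the sample size, the primary analysis or eligibility, and this review takes no position on which rule is clinically right.

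**What to change.** Reconcile the two lists in the DILI monitoring part of Section 10.B by stating which one governs when an ALT value meets both. If the redacted text already says so, repeat it or refer to it there. The choice is for the investigators and the DSMB. The cost is a short protocol amendment agreed with the DSMB; no visit, assessment or analysis changes.
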